11.2. Analysis Populations

The Intent to Treat (ITT) population is defined as all subjects who are randomized. The Safety population is defined as all randomized subjects who applied at least 1 application of study medication. The Per-Protocol (PP) population is defined as all subjects who are randomized and do not have any major protocol violations. Major protocol violations are defined as:

1. Inclusion or Exclusion criteria not met
2. Concomitant medications taken during the study that interfere with efficacy
3. Did not apply at least 75% of study medication
4. Did not complete Week 24 (Visit 10).

11.3. Demographic and Baseline Characteristics

Subject demographic and baseline characteristics, including medical and alopecia history, prior medications and therapies and physical examination findings will be summarized using descriptive statistics.

For continuous variables, descriptive statistics (number, mean, standard deviation, standard error, median, minimum, and maximum) will be provided. For categorical variables, subject counts and percentages will be provided. Categories for missing data will be presented, if necessary.

11.4. Efficacy Analyses

11.4.1. Primary Efficacy Analyses

The primary efficacy variable will be the percent change from baseline in the SALT score at Week 24 (Visit 10). This represents the percentage of hair regrowth. It will be calculated as the mean of the changes from baseline (Visit 2) SALT score to Week 24 (Visit 10) SALT score, divided by the baseline SALT score and expressed as a percentage. Missing data for the primary endpoint will be imputed using Last Observation Carried Forward (LOCF) methodology. The analysis will be conducted on the relative percent change from baseline over time including all visits using a mixed effect model repeated measures (MMRM). The adjusted mean (LS Mean) for percent change from baseline in the SALT score at each visit, estimated from the MMRM, with the estimated standard error and 95% confidence interval (CI), will be presented in tabular and graphic

format. The difference in the adjusted means between treatment groups and the associated 95% CI of the difference will be provided. No adjustment for multiplicity will be made. The model will include fixed effect terms for treatment, study visit, baseline SALT score group (<50, ≥ 50), and treatment by SALT group interaction. The primary analysis will be based on the Intent-to-Treat (ITT) population. Statistical significance for primary efficacy endpoint will be declared if at least one treatment group comparison at the Week 24 visit has a two-sided p-value less than or equal to 0.05.

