4. STUDY OBJECTIVES

4.1. Primary Objective

The primary objective is to assess the safety, tolerability and efficacy of ATI-50002 Topical Solution, 0.46% and 0.12% compared to vehicle in subjects with stable patchy alopecia areata (AA).

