8.1. Assessments of Efficacy

8.1.1. Severity Alopecia Tool (SALT) Score

The SALT score is a measurement of the amount of scalp without any terminal hair. The investigator will assess the SALT score using an iPad provided by Aclaris at baseline and monthly during the study. The SALT score must be determined prior to the ALODEX score. At the baseline visit (Visit 2), the SALT score must be determined prior to randomization and the score must be at least 15% to 95% total scalp hair loss. Equipment, supplies, training and the detailed Reference Guide will be provided to the investigational site prior to the initiation of subject enrollment.

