13. ETHICS AND GENERAL STUDY CONDUCT CONSIDERATIONS

13.1. Institutional Review Board (IRB)/Ethics Committee (EC)

This protocol, informed consent/ assent form, any information provided to subjects, subject-recruiting advertisements, and any amendments to these items will receive IRB/EC approval prior to use.

The IRB/EC must receive a copy of the Investigator's Brochure, all protocol amendments, safety reports and other study related information as required by regulation or the IRB/EC procedures.

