#### **3.3.3. Multiple Testing and Comparisons**

There are no planned adjustments for multiple comparisons.

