## **5. STATISTICAL METHODS**

Descriptive statistical methods will also be used to summarize the data from this study, with hypothesis testing performed for the primary and key secondary efficacy endpoints. Unless stated otherwise, the term “descriptive statistics” refers to number of subjects, mean, median, standard deviation, minimum, and maximum for continuous data, and frequencies and percentages for categorical data. For categorical variables, the denominator of percentages will be the number of subjects in the treatment group, except for those collected by study visit and/or scheduled time point, in which case the denominator of percentages will be the number of subjects with a non-missing value at the visit and/or the scheduled time point. If a different denominator is used, this will be identified in the summary table.

All data collected during the study will be included in data listings. Unless otherwise noted, the data will be sorted first by treatment group, subject number, and then by date within each subject number. Assessments indicated as ‘Not Done’ will not be included in the listings.

The term ‘treatment group’ refers to ATI-50002 active groups and matching Vehicle group.

All statistical testing will be two-sided and will be performed using a significance (alpha) level of 0.05 unless otherwise stated. P-values will be presented to three decimal places. For the efficacy endpoints, the ATI-50002 treatment groups will be tested versus vehicle via statistical inference.

The statistical analyses will be conducted with the SAS® software package version 9.4 or higher. All analyses will be subject to formal verification procedures. Specifically, results will be independently verified by a second programmer/statistician or independently hand-checked prior to issuance of the draft statistical report. All documents will be reviewed by the lead statistician to ensure accuracy and consistency.

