## **5.2. EFFICACY ANALYSIS**

### **5.2.1. Primary Efficacy Endpoint**

The primary efficacy variable will be the mean percent change from baseline in the SALT score at Week 24 (Visit 10).

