### **5.2.2. Primary Efficacy Analysis**

Descriptive statistics for the SALT score, change, and percent change from baseline will be presented for each scheduled analysis visit. Percent change from baseline in SALT over time up to Week 24 will be analyzed using a mixed effect for repeated measures (MMRM) model. This primary analysis will utilize the score with imputation for LOCF and will be based on the ITT population. The model will include fixed effect terms for treatment, study visit, baseline SALT score group (<50, >=50), and treatment by SALT group interaction. Within-subject variability will be modeled using a compound symmetry covariance structure. The least squares mean (LS Mean) percent change from baseline in the SALT score at each visit, estimated from the MMRM model, with the estimated standard error and 95% confidence interval (CI), will be presented in tabular and graphic format. The difference in the adjusted means between treatment groups and the associated 95% CI of the difference will be provided.

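### Should the rule for declaring the primary endpoint significant also say that the difference must favour ATI-50002 over vehicle?

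*Protocol*

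**What the plan says.** Protocol Section 11.4.1, repeated in the synopsis, declares the primary endpoint statistically significant if "at least one treatment group comparison at the Week 24 visit has a two-sided p-value less than or equal to 0.05". Neither place names the comparator or the direction. The same section says that no multiplicity adjustment is made, that the percent change represents hair regrowth, and that differences in adjusted means are given with 95% confidence intervals.

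Other sections supply most of what the rule omits:

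- Protocol Section 4.1 gives the objective as assessing "efficacy of ATI-50002 Topical Solution, 0.46% and 0.12% compared to vehicle". SAP Section 2 agrees.
- SAP Section 5 makes all testing two-sided at 0.05 and states that, for the efficacy endpoints, "the ATI-50002 treatment groups will be tested versus vehicle via statistical inference".
- SAP Section 3.3.3 says: "There are no planned adjustments for multiple comparisons".
- Protocol Section 8.1.1 fixes which way is better: "The SALT score is a measurement of the amount of scalp without any terminal hair". A lower score is better.
- SAP Section 3.3.6 defines change as the visit value minus baseline, so a more negative percent change means more regrowth.

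SAP Sections 5.2.1 and 5.2.2 give the endpoint and the model. They repeat the reporting of differences and intervals but state no declaration rule.

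**The concern.** The protocol sentence is the only formal statement of when the primary endpoint is declared significant. With three arms there are three pairwise comparisons, one of them between the two strengths. A two-sided p-value carries no direction. Taken literally, the rule could be met by 0.46% differing from 0.12%, or by vehicle beating a strength. A report could then announce a significant primary endpoint although neither strength had beaten vehicle, which is what the objective asks. The power statement adds to the doubt, because it refers to a difference between any two groups. SAP Section 6 says that its analyses are consistent with the protocol, so it records no amendment of the rule.

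**Working it through.** **Inputs.** From Protocol Section 11.1 and SAP Section 3.1: 40 per group, SD 38, difference 24 points, 80% power. From SAP Section 5: two-sided alpha 0.05.

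**The plan's own power figure.** The standard error of a difference is 38 × √(2/40) = 8.50, and 24/8.50 = 2.82. The normal approximation gives Φ(2.82 − 1.96) = 0.806. The t test gives 0.797 with 78 df, and 0.800 with 117 df (variance pooled over three arms). The stated 80% reproduces.

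**How often the rule is met when nothing works.** Take simple pairwise t tests with pooled variance, 117 df and critical value 1.980. The two active arms share one vehicle arm, so the two contrasts have correlation 0.5.

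| Event, no true effect | Probability |
|---|---|
| One given comparison significant in favour of active | 0.0250 |
| Either comparison with vehicle significant, any direction | 0.0905 |
| At least one strength significantly better than vehicle | 0.0453 |
| Rule met, but only by vehicle being better | 0.0452 |
| Any of the three pairs significant, any direction | about 0.12 |

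For the second row, 0.05 + 0.05 = 0.10, less about 0.0095 for both being significant together. For the third, 0.025 + 0.025 = 0.05, less about 0.0047. The fourth is 0.0905 − 0.0453 = 0.0452.

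**The planned model.** SAP Section 5.2.2 uses compound symmetry and no treatment-by-visit term. If every subject has all six visits after LOCF, the treatment contrast reduces to a contrast of subject means over those visits. Simulation with no effect covered SALT-group splits of 50:50 and 70:30, and a true covariance that was either compound symmetry or AR(1) with growing SD. The rule was met in 8.8% to 9.4% of trials, and in 4.5% to 4.7% with a strength better than vehicle. The range includes both choices of degrees of freedom, because the SAP names no method. The picture is the same as with simple tests.

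**What writing in the direction would do when the drug works** (simple tests, comparisons with vehicle only).

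| True state | Rule as written | With direction required |
|---|---|---|
| Both strengths 24 points better | 0.912 | 0.912 |
| One strength 24 points better, the other no effect | 0.8156 | 0.8002 |

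The difference in the second row, 0.8156 − 0.8002 = 0.0154, consists of trials in which the only significant result is the ineffective strength doing worse than vehicle. Power per comparison stays at 80%.

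**What depends on the declaration.** There is no testing hierarchy for it to open (SAP Section 3.3.3). The end-of-double-blind analysis runs once the blinded period is complete (SAP Section 3.4.1). Entry to the open-label extension does not depend on the primary result (Protocol Section 5.5.1), and everyone there receives 0.46% (Protocol Section 7.2). Sample size was set by feasibility (Protocol Section 11.1).

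**The case for a change.** The best argument for a change is that a pre-specified rule should not rely on inference, that the direction takes only a few words, and that a sentence added after unblinding would look data-driven. Protocol Version 9.0 was itself issued partly to clarify the primary analysis. SAP Section 5 does not say that active versus vehicle are the only tests. It is also true that no passage in either document states the direction.

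That last point stands as a remark on wording. The rest carries little weight. An analyst following SAP Section 5 would test the two strengths against vehicle and report signed differences with intervals. To count a result in vehicle's favour as support for the drug, a reader would have to ignore the sign in the same table. The roughly 12% figure needs the strength-against-strength comparison, which SAP Section 5 does not plan. That half of the 9.0% favours vehicle is the symmetry of two-sided testing. The step from 2.5% to 4.5% comes from having two unadjusted comparisons, which the plan discloses and which a direction clause would leave unchanged.

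An added sentence could also bring new trouble. If it defined benefit as a greater reduction in SALT score, it would point to a secondary endpoint, because the primary variable is percent change. With baselines from 15 to 95, the two can rank arms differently. Placed in the SAP alone, it would leave two differently worded rules while SAP Section 6 claims consistency.

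**Conclusion.** No change to the plan follows. The comparator is settled by SAP Section 5 and the objective. The direction is unwritten, but the objective, the meaning of the SALT score and the required signed differences supply it. The gap touches only the label attached to a result. No estimate, interval, p-value or per-comparison power depends on it, and no later step in the trial does either.

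In size, with no true effect, about 4.5% of trials would meet the rule only because vehicle did better, and the reported difference would show this. With one effective strength, about 1.5 points of declaration probability are at issue; with both effective, essentially none.

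These figures assume equal arms of 40, SD 38 and, for the power values, simple pairwise tests. The planned-model figures assume complete visits after LOCF. The conclusion also assumes that the report shows the differences and intervals, as both documents require.

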11.4.2. Secondary Efficacy Analyses

A secondary sensitivity analysis of the primary endpoint will be conducted using the PP population. This analysis will use the same methodology as described for the primary analysis just applied to the PP population.

The secondary efficacy endpoints include: the percent change from baseline in the ALODEX score (percent regrowth); the mean change from baseline in SALT and the mean change from baseline in ALODEX, the proportion of subjects achieving a $\geq 50\%$ hair regrowth compared with baseline using a separate model for SALT and for ALODEX scores; change from baseline in the AAA (Clinician and Subject), PhGIS, SGIS, AIA, treatment satisfaction questionnaires; and DLQI. Various secondary responder efficacy endpoints will be defined based upon the SALT score, the ALODEX scores and the AAA (Clinician and Subject) questionnaires. Details of these responder definitions will be specified in the statistical analysis plan (SAP). Global Impression of Change (Clinician and Subject) at Week 24 (Visit 10) will be used in the psychometric evaluation of the scores from the AAA (CR and SR), respectively. All secondary efficacy endpoints will be analyzed using the ITT population. The analysis of the percent change in ALODEX score analysis will use the same methodology as specified for the primary efficacy analysis. Other parameters will be analyzed as detailed in the SAP.

11.5. Safety Analyses

Safety analyses will include descriptive statistics calculated on the safety parameters using the safety population. The proportion of subjects with treatment-emergent adverse events will be tabulated and presented by treatment and Medical Dictionary for Regulatory Activities (MedDRA) System Organ Class. Vital signs and clinically significant abnormal laboratory results will also be tabulated and presented by treatment group.

Data from all randomized subjects will be presented and summarized. Safety summaries by study treatment group will include listings by study medication of adverse events incidences within each MedDRA System Organ Class, and changes from pre-application values in vital signs. Adverse event summaries will be presented by study medication showing the proportion of subjects experiencing adverse events, both overall and by MedDRA System Organ Class.

11.6. Open-Label Extension Analyses

OLE endpoints will include safety variables, efficacy variables [(change from baseline in SALT, ALODEX at long-term visits), (change from baseline in AAA-SR, AAA-CR, and SGITS)].

11.7. Exploratory Biomarker Analyses (Select Sites Only)

11.7.1. ALADIN Scores (Select Sites Only)

The cytotoxic T-lymphocyte infiltration (CTL), Interferon (IFN-gamma), and hair keratin (KRT) ALADIN scores will be calculated for each scalp biopsy sample as described in (Xing et al, 2014, Jabbari 2016). Change in ALADIN scores within individual subjects will be assessed between Baseline (Visit 2), Week 4 (Visit 5), and Week 24 (Visit 10).

11.7.2. Scalp Biopsy for Histology and Immunology (Select Sites Only)

Scalp punch-biopsies will be formalin-fixed and paraffin-embedded and will be sectioned both vertically and horizontally by a qualified dermatopathologist. Specimens will be stained with hematoxylin and eosin (H&E) for “routine” histopathologic evaluation that will include (but is not limited to) diagnosis and evaluation of the presence, quantity, location, and quality of any hair, hair follicles, and inflammatory infiltrate present. Additionally, immunohistochemical (IHC) stains will be employed to identify immune cell populations (e.g., Lymphocytes, cytotoxic T-lymphocytes (CTLs)), and hair-specific keratins. IHC stains to assess inflammatory responses will include but not be limited to CD8, HLA-DR and ICAM-1. Data will be presented as percent change from baseline in the number of cells/ high power field in regions of interest (peribulbar areas) and in percent change from baseline in the number of cells/mm².

11.7.3. Blood for Immunology (Select Sites Only)

Blood samples will be stained with cell surface antibodies for fluorescence acquisition cell sorting (FAC) analysis. FACS experiments will allow for assessment of the subset and activation status of immune cells involved in AA.

11.7.4. Clinical Correlative Studies (Select Sites Only)

Previous studies in human AA have reported increased NKG2DL expression and augmented expression of IFN response genes in the target hair follicle end organ, and elevated NKG2D expression in circulating CD8 T-cells and NK cells (Ito et al, 2008; Petukhova et al, 2010).

The study will include assessment at select sites of AA biomarkers at baseline and during treatment to correlate treatment and disease status with:

1. Histological improvement with reduced T-cell peribulbar infiltrates.
2. Declines in circulating and peribulbar CD8+NKG2D+ infiltration and in follicular hair follicle NKG2DL expression.
3. Reduced IFN inflammatory biomarkers in the skin and blood.

12. TRAINING, MONITORING, DATA MANAGEMENT AND QUALITY ASSURANCE

12.1. Training

For each investigational center, there will be an initiation visit prior to enrolling any study subjects.

It is strongly recommended that all investigators, other evaluators, study nurses, study coordinators or other applicable personnel attend this visit. During this visit, participants will be trained to the protocol, study specific procedures, and the eCRFs. Those unable to attend the initiation visit must receive on-site training from an appropriately trained individual prior to participating in any of the procedures and evaluations in this study.

Clinical Research Associates (CRAs) and other applicable personnel will be trained prior to study initiation to familiarize CRAs with the disease, the Standard Operating Procedures (SOPs), the protocol and other study specific items. Team organization, communication and operational issues will also be discussed.

Aclaris Therapeutics, Inc. will provide an investigational center file to each center.

12.2. Monitoring

The conduct of the study will be closely monitored by representatives of Aclaris Therapeutics, Inc. to verify adherence to ICH Good Clinical Practice (GCP) guidelines, and applicable SOPs. Reports of these verifications will be archived with the study report. The investigator will allow the Aclaris Therapeutics, Inc. representative's designee and/or any regulatory agency to have direct access to all study records, eCRFs, corresponding subject medical records, study medication-dispensing records and study medication storage area, and any other documents considered source documentation. The investigator also agrees to assist the representative, if required.

12.3. Data Management

Data-management activities of this study will be subcontracted. Edit checks and review processes will be performed by the sub-contractor until all data clarifications are resolved. The data will be exported to be stored in SAS datasets (or equivalent) by the sub-contractor. After all data clarifications are resolved and subject's evaluability is determined, the database will be locked.

12.4. Quality Assurance

The study is conducted under the sponsorship of Aclaris Therapeutics, Inc. in compliance with the applicable regulatory requirements as well as applicable ICH guidelines, Declaration of Helsinki, and in respect of the Aclaris Therapeutics, Inc. and/or sub-contractor SOPs for study conduct and monitoring.

Audits may be carried out by Aclaris Therapeutics, Inc. or Aclaris Therapeutics, Inc.'s representatives, and inspections may be performed by regulatory authorities or IRB/ECs before, during or after the study. The investigator will provide the auditing/inspecting group direct access to all study records (e.g., eCRFs, subject medical records, study medication dispensing records) and the investigational center study facilities. The investigator and study staff will be available and will assist the auditing/inspecting groups as appropriate.

13. ETHICS AND GENERAL STUDY CONDUCT CONSIDERATIONS

13.1. Institutional Review Board (IRB)/Ethics Committee (EC)

This protocol, informed consent/ assent form, any information provided to subjects, subject-recruiting advertisements, and any amendments to these items will receive IRB/EC approval prior to use.

The IRB/EC must receive a copy of the Investigator's Brochure, all protocol amendments, safety reports and other study related information as required by regulation or the IRB/EC procedures.

13.2. Ethical Conduct of the Study

The rights, safety and well-being of the subjects are the most important considerations in this study and take priority over the interests of society and science.

This study will be conducted in accordance with the ethical principles originating from the Declaration of Helsinki, the ICH E6 GCP guideline, local regulatory requirements and, at US investigational centers, in compliance with the HIPAA. The study will be conducted in compliance with the IRB/EC approved version of the protocol and any applicable amendments.

